5. METHODS

5.1 Study parameters/endpoints

5.1.1 Main study parameter/endpoint

Disability is expressed by the WHODAS 2.0, which is based on difficulties experienced by the respondent in different functional domains including, cognition, mobility, self-care, getting along, life activities and participation during the previous 30 days. Disability is defined as a decrement in each functioning domain corresponding to score between 0% and 100%, in which no disability stands for a score of 0% and full disability represents a score of 100%, including death. The WHODAS 2.0 is easy to use and patient centered (see F1 for the questionnaire). In a validation study including noncardiac surgical patients, the WHODAS 2.0 has been found to be a clinically acceptable, valid, reliable and responsive instrument for measuring postoperative disability²⁷.

5.1.2 Secondary study parameters/endpoints

- *Disability free survival* is defined as being alive with a WHODAS score $\leq 25\%$ and no increase of the pre-operative score $\geq 25\%$ at 6 months after surgery.
- *An in-hospital major adverse postoperative events (MAPE)*, which could be distinguished in:
 - o *Major adverse cardiovascular event (MACE)*, which is defined as the composite endpoint of:
 - Cardiovascular death, defined as death resulting from an acute myocardial infarction, sudden cardiac death, death due to heart failure, death due to stroke, and any acute death unconfirmed yet probably due to a cardiovascular cause.
 - Non-fatal myocardial infarction, defined in accordance to the third universal definition of myocardial infarction¹⁰.
 - Non-fatal cardiac arrest.
 - Non-fatal ventricular fibrillation.
 - Ventricular arrhythmia with hemodynamic compromise.
 - Atrial fibrillation requiring cardioversion.
 - Pulmonary embolism, defined as a new thrombus within the pulmonary arterial system confirmed on CTA
 - Stroke confirmed on CT.
 - o *Noncardiac MAPE*, which is a composite outcome consisting of:
 - Respiratory failure including pneumonia and hypoxia or hypercapnia leading to ICU admission for respiratory support

- Sepsis and/or systemic inflammatory response syndrome (SIRS), defined as life-threatening organ dysfunction caused by a dysregulated host response to infection²⁸.
- Renal failure, defined as AKIN criteria or renal replacement therapy.
- Unplanned ICU admission
- Unplanned medium care admission
- Reoperation
- *Length of hospital stay, defined as the number of days from the end of surgery until day of discharge*
- *In-hospital all-cause mortality*
- *6-month all-cause mortality*
- *6-month MACE*

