beginning of the study, the estimated inclusion time is one year with six months follow-up resulting in a total study time of 18 months.

Main study parameters/endpoints:**Primary end points:**

Disability is expressed in terms of the WHODAS 2.0 which is based on different functional domains, including cognition, mobility, self-care, getting along, life activities and participation.

Secondary endpoints:

- *Disability free survival* is defined as being alive with a WHODAS 2.0 score $\leq 25\%$ and no increase of the preoperative score $\geq 25\%$ at 6 months after surgery.
- *An in-hospital major adverse postoperative events (MAPE)*, which could be distinguished in:
 - o *Major adverse cardiac event (MACE)*, which is defined as the composite endpoint of cardiovascular death, non-fatal myocardial infarction, non-fatal cardiac arrest, non-fatal ventricular fibrillation, non-fatal ventricular hemodynamic compromise and atrial fibrillation requiring cardioversion.
 - o *Noncardiac MAPE*, which is defined as a composite outcome consisting of respiratory disorders (including pneumonia and respiratory failure), pulmonary embolism, sepsis and/or systemic inflammatory response syndrome (SIRS), renal failure, reoperation and unplanned ICU admission.
- *In hospital all-cause mortality*
- *Length of hospital stay*
- *6-month MACE*
- *6-month all-cause mortality*

Nature and extent of the burden and risks associated with participation, benefit and group**relatedness:**

In addition to routine care, patients will be asked to fill out the WHODAS 2.0 before surgery and additional blood will be drawn (7 cc in total) before induction of anesthesia. Postoperatively, extra blood will be taken up to three days after surgery (7 cc in total each time) during routine blood draws. At postoperative day 2, an electrocardiogram (ECG) and transthoracic echo (TTE) will be performed. Six months after surgery, patients will be asked to fill out the WHODAS 2.0 for the second time and their GPs will be approached to assess whether clinically relevant events have occurred. The study is associated with a negligible risk as only noninvasive imaging procedures will be performed

and blood will be drawn. The treating physician will be notified in case any unexpected findings from the ECG and TTE are observed meaning that participation to this study could lead to early recognition of heart disease.

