2.2 Secondary objectives

1. To investigate and compare the independent prognostic effect of the different PMI phenotypes (myocardial infarction and NITE) and noncardiac MAPE on disability free survival in patients undergoing elective noncardiac surgery.
2. To examine whether (combinations of) perioperatively measured cardiac biomarkers are associated with in-hospital major adverse postoperative events (MAPE) in patients undergoing elective noncardiac surgery. MAPE are divided in different subtypes, including:
 - a. Major adverse cardiovascular events (MACE), which is defined as the composite endpoint of cardiovascular death, non-fatal myocardial infarction, non-fatal cardiac arrest, non-fatal ventricular fibrillation, ventricular hemodynamic compromise, atrial fibrillation requiring cardioversion, pulmonary embolism and stroke.
 - b. Noncardiac major adverse postoperative events (MAPE) including sepsis, renal failure, unexpected ICU admission and respiratory failure.
 - c. All-cause mortality
3. To examine whether (combinations of) perioperatively measured cardiac biomarkers are associated with 6-month MACE and all-cause mortality in patients undergoing elective noncardiac surgery.
4. To assess the added value of the perioperatively measured biomarkers on top of the currently used Revised Cardiac Risk Index (RCRI) to predict major adverse cardiac events (MACE) after noncardiac surgery.

[figure not shown]

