5.1.3 Other study parameters

- Baseline characteristics including:
 - Demographics, i.e. age, gender, BMI, smoking status, American Society of Anesthesiologists class (ASA).
 - Comorbidities, including history of the following diseases: myocardial infarction, cerebrovascular disease, congestive heart failure and cancer. Currently diagnosed with: diabetes, coronary artery disease, chronic renal failure, cancer, chronic obstructive pulmonary disease, peripheral vascular disease, and hypertension.
 - Medication use, including beta blockers, angiotensin converting enzyme inhibitors, calcium blockers, diuretics, statins, insulin, oral antidiabetics.
 - Surgical history, including coronary revascularization, pacemaker or implantable cardioverter defibrillator (ICD).
 - Laboratory results of preoperatively measured blood biomarkers, i.e. hsTroponin, C-reactive protein (CRP), brain natriuretic peptide (BNP), hemoglobin (Hb) and creatinine in blood. Imaging biomarkers are electrocardiogram (ECG) and transthoracic echocardiogram (TTE).
 - Referral of the screening anesthesiologist at the preanesthesia consultation clinic to a cardiologist or other specialist before surgery
 - Preoperative WHODAS 2.0
- Intraoperative:
 - Anesthesia related including type of anesthesia (general or spinal), vital signs (i.e. blood pressure, heart rate, eCO2).

- Surgical related factors: surgical risk, surgical specialty, blood loss, number of blood transfusions and fluid balance.
- Postoperative:
 - Troponin I monitoring at postoperative day 1-3 as being part of routine care.
 - Laboratory results of postoperative measured blood biomarkers, i.e. hsTroponin, CRP, BNP, Hb and creatinine in blood on postoperative day 1-3. Imaging biomarkers (ECG and TTE) on postoperative day 2.
 - Rehospitalization within 6 months after surgery.

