- Answering the WHODAS 2.0 questionnaire and a questionnaire regarding patient's health since the surgery (see F1. Vragenlijst 6 maanden follow up and F1. Vragenlijst WHODAS). Both questionnaires will be sent to the patient's home address and in the accompanying letter, a date with time will be mentioned during which patients could expect a telephone call by the researcher. The questionnaires will be taken off by telephone. In case of nonresponse, the researcher will approach the patient at another time to keep the response rate as high as possible.

- Approaching the patient's general practitioner to obtain information regarding postoperative events in the previous 6 months after surgery. This information will include clinically relevant events, such as MACE, hospital admission/consultation and change in medication prescription. In case patients are admitted or consulted at a hospital, the corresponding treating physician will be approached as well for clinically relevant information.

Before sending the questionnaires to the patient's home address, the GBA (Gemeentelijke Basisadministratie) will be used to find out whether the patient is still alive, to avoid sending questionnaires and calling patients who have deceased. Follow up will end after completion of both questionnaires. All results will be merged to the preoperative patient characteristics and biomarker data using the corresponding study number and hospital identifier.

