- The added prognostic value of each of the biomarkers (or combinations of biomarkers) will be tested to predict MACE, both in-hospital and at 6-months. The biomarkers will be analyzed as continuous variables and using predefined clinical thresholds to define whether that particular biomarker is elevated. Multivariable logistic regression analyses will be performed using the predictors of the RCRI (i.e. high risk surgery, history of cerebrovascular disease, history of myocardial infarction, congestive heart failure, elevated creatinine and insulin dependent diabetes) as predictors together with the addition of elevation in biomarkers. Discrimination and calibration of the prediction models will be assessed using the c-statistic, Hosmer-Lemeshow test. The net reclassification index (NRI) and the Integrated Discrimination Index (IDI) will be calculated to quantify how well the updated RCRI reclassifies patients as compared to the traditional RCRI.

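### Section 5.1.2 accepts stroke only on CT and pulmonary embolism only on CTA, so non-fatal events proven another way do not count as MACE through those components, although the objectives set no such limit

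*Combined protocol and SAP*

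**What the plan says.** Section 5.1.2 is the only place where the MACE components are defined in detail. Two of them carry a single imaging condition:

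- Embolism: "Pulmonary embolism, defined as a new thrombus within the pulmonary arterial system confirmed on CTA".
- Stroke: "Stroke confirmed on CT".

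Objective 2a in Section 2.2 ends its list of MACE components with "ventricular hemodynamic compromise, atrial fibrillation requiring cardioversion, pulmonary embolism and stroke" and sets no imaging condition. The Summary's objectives do the same. The Summary's endpoint list differs from both. It leaves stroke out of MACE and places embolism under noncardiac MAPE: "respiratory disorders (including pneumonia and respiratory failure), pulmonary embolism, sepsis and/or systemic inflammatory response syndrome (SIRS), renal failure, reoperation and unplanned ICU admission".

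Deaths are handled separately. The cardiovascular-death component of Section 5.1.2 needs no imaging and includes "death due to stroke, and any acute death unconfirmed yet probably due to a cardiovascular cause".

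Section 5.1.2 also lists 6-month MACE, with no separate definition. Section 5.3 collects those events from the patient and the general practitioner, and adds: "In case patients are admitted or consulted at a hospital, the corresponding treating physician will be approached as well for clinically relevant information".

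**The concern.** The rule that derives the outcome is narrower than the outcome named in the objectives. MACE is the outcome in objectives 2a, 3 and 4. Section 7.3 models it by logistic regression, in hospital and at 6 months, and uses it to judge what the biomarkers add to the RCRI.

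A non-fatal stroke with a negative CT and an infarct on MRI fails the stroke item. A non-fatal embolism shown only on a ventilation-perfusion scan fails the embolism item. The exposure to this is greater at 6 months, because the study does not control which imaging another hospital uses. Two abstractors could also score the same report differently, one by the objective and the other by Section 5.1.2.

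There is a further question about creatinine. It is among the measured biomarkers ("hsTroponin, CRP, BNP, Hb and creatinine in blood on postoperative day 1-3") and also an RCRI predictor ("high risk surgery, history of cerebrovascular disease, history of myocardial infarction, congestive heart failure, elevated creatinine and insulin dependent diabetes"). If the chance of having a CTA depended on renal function, the missed embolisms would depend on one of the exposures under test.

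**Working it through.** **Does any other text widen the rule?** No. Sections 2.2, 5.1.2, 5.3 and 7.3 name no other modality for stroke or embolism and describe no outcome adjudication. The only independent reading is of the study ECG and TTE (Section 5.3).

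**Which events are affected?** Mainly non-fatal ones. Fatal stroke is named under cardiovascular death. Fatal embolism is not named, but probably falls under the closing catch-all of that item.

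**How many events?** There is no plan figure to reproduce, because the documents give no stroke or embolism rate.

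- From the plan: PMI in 11.0% (Section 4.4), about one third of it infarction (Section 1). Infarctions per 1,000 = 1,000 × 0.11 / 3 = 36.7.
- Assumed: stroke in 0.3% to 1% of patients and embolism in 0.3% to 1%, so 6 to 20 events per 1,000. Of these, 20% to 50% are not shown on CT or CTA.
- Lost: 6 × 0.2 = 1.2 to 20 × 0.5 = 10 per 1,000.
- Share of infarction + stroke + embolism: 1.2 / 42.7 = 2.8% to 10 / 56.7 = 17.6%.

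These shares err high. The denominator omits cardiovascular death, cardiac arrest, the arrhythmia components and cardioverted atrial fibrillation. Some of the affected patients would qualify through another component. The top figure also needs both assumptions at their maximum.

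**Loss unrelated to a biomarker.** With no false positives, the risk ratio is unchanged. For the odds ratio, take assumed risks of 10% and 5% and lose 18% of events in both groups:

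- Before: (0.10/0.90) / (0.05/0.95) = 2.11.
- After: (0.082/0.918) / (0.041/0.959) = 2.09.

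The cost is precision. With uncommon events the standard error grows roughly as 1/√(share kept): 1/√0.972 = 1.01 to 1/√0.824 = 1.10.

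**Loss related to creatinine, if it exists.** Assume CTA confirms 50% to 70% of embolisms with high creatinine and 90% otherwise, that the true risk is equal in both groups, and that strokes are fully counted. The factor on the composite relative risk is (events counted, high creatinine) / (events counted, others):

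| Stroke and embolism, each per 1,000 | 50% confirmed | 70% confirmed |
|---|---|---|
| 3 | (36.7+3+1.5)/(36.7+3+2.7) = 0.97 | (36.7+3+2.1)/42.4 = 0.99 |
| 10 | (36.7+10+5)/(36.7+10+9) = 0.93 | (36.7+10+7)/55.7 = 0.96 |

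**A less favourable scenario, all inputs assumed.** Embolism occurs in 0.5% to 2% of patients with normal creatinine and in twice that share with high creatinine. High creatinine is present in 10% to 20% of patients. Embolism is not proven by CTA in 5% to 10% (normal) versus 20% to 50% (high). The true odds ratio of creatinine for other MACE is 2. Then 0.4 to 4.5 of 46 to 67 MACE events are lost. The creatinine odds ratio falls from 2.01–2.04 to 1.69–1.97, a factor between 1.69/2.04 = 0.83 and 1.97/2.01 = 0.98.

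**The case against.** Requiring objective imaging is a defensible choice that favours specificity, and MACE is a secondary endpoint. Both points stand. They argue for keeping objective proof, but not for limiting it to one modality.

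A reader might infer four stronger things that the documents do not support:

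- *Events found at autopsy are lost.* Fatal stroke is explicitly cardiovascular death, and fatal embolism is probably caught by the closing clause. What remains is a small ambiguity: that clause speaks of unconfirmed deaths, and an autopsy-proven embolism is confirmed.
- *Affected patients are scored as free of MACE.* They miss one component of a composite and may meet another.
- *All biomarker associations are attenuated.* Loss unrelated to the biomarker barely moves the odds ratio. Nothing in the documents suggests differential loss for troponin, BNP, CRP or hemoglobin.
- *The creatinine association is materially biased.* No section links the choice of imaging to renal function. The assumed confirmation rates do imply a factor of 0.5/0.9 = 0.56 to 0.7/0.9 = 0.78 for embolism alone, but the plan models the composite and has no embolism-only regression.

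It is also fair to object that the plan never says the imaging conditions govern 6-month MACE. That is the natural reading, because no other definition is given, but it is an inference. The plan should settle it.

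**Conclusion.** The point holds in a limited form. A stated rule in Section 5.1.2 excludes non-fatal strokes and embolisms proven by other objective means, and it is narrower than the objectives it serves. The same would apply at 6 months if no other definition is intended.

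The main consequence is a MACE proportion that is too low, by roughly 0.1 to 1.0 percentage points under the assumed rates (1.2 to 10 per 1,000), with standard errors up to about 10% larger. A downward bias for creatinine is conditional on an imaging pattern that the documents do not state. If it exists, it is about 1% to 7% on the composite relative risk with equal true risk, and larger only if embolism is itself commoner with high creatinine.

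All of these sizes rest on assumed rates. The WHODAS primary analysis is not affected. The change is worth making because it is cheap, not because the expected harm is large.

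**What to change.** 1. First settle which composite each event belongs to. The Summary's endpoint list (embolism in noncardiac MAPE, stroke in neither composite) must be reconciled with Sections 2.2 and 5.1.2.
2. In Section 5.1.2, define stroke as confirmed on CT or MRI, or at autopsy. Define pulmonary embolism as confirmed on CTA, ventilation-perfusion scan or pulmonary angiography, or at autopsy. Do not add a requirement for a neurologist's diagnosis, which could itself exclude events.
3. State that these definitions apply to in-hospital and 6-month MACE and to both centres, because Section 4.4 pools the Utrecht and Toronto data.
4. Record the confirming modality for each event, and report MACE under the CT/CTA-only definition as a sensitivity analysis.

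The cost is a wording change, one CRF field and agreement between the two centres. No extra tests are needed, because information from treating physicians is already requested. The downside is slightly less uniform confirmation across events, which the sensitivity analysis makes visible.

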2. OBJECTIVES

2.1 Primary objective

To investigate and compare the independent prognostic effect of the different PMI phenotypes (myocardial infarction and NITE) and noncardiac MAPE on disability in patients undergoing elective noncardiac surgery.

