Hospital admittance and intraoperative data collection

For patients who agreed on study participation during the telephone call one week before surgery, informed consent will be signed by the patient and study investigator. If a patient decides to decline study participation at this point, this patient will receive routine care as usual. The treating anesthesiologist will be informed about participation and 7 cc blood will be drawn at the operation theatre immediately before induction of anesthesia. Blood will be collected, processed and stored at the Centrale Biobank (CBB) with corresponding study number. Blood biomarkers will be considered preoperative baseline values. During surgery, the following data will be collected:

- Vital signs, i.e. blood pressure, heart rate and ET-CO₂.
- Blood loss and number of blood transfusions
- Duration of surgery

Collection of intraoperative data is part of routine clinical care; no study related procedures will be conducted.

Postoperative in hospital stay

At postoperative day 1-3, the following procedures will be performed:

- Extra blood (7 cc each time) will be drawn during the standard blood sampling rounds in the morning. Blood will be processed and stored at the CBB.
- At postoperative day 2, an ECG and TTE will be performed by certified study personnel and uploaded at the local electronic health record (EHR) and a digital databank.
- In-hospital MAPE, such as MACE, unplanned ICU admission, respiratory disorders, renal failure, sepsis and/or SIRS and mortality will be monitored.

At the UMCU, troponin-I is routinely monitored in all patients, aged ≥ 60 years, undergoing major noncardiac surgery. In case troponin-I is elevated, routine (i.e. non-study related) hospital protocol procedures involve an ECG and consultation by an anesthesiologist. The anesthesiologist could consult a cardiologist for further examination. Additional diagnostic tests or initiation of therapy is

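### Noncardiac MAPE counts any unplanned ICU or medium care admission, so cardiac admissions are double-coded and the comparison of MI, NITE and noncardiac MAPE is blurred

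*Combined protocol and SAP*

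**What the plan says.** The primary objective (section 2.1) is "To investigate and compare the independent prognostic effect of the different PMI phenotypes (myocardial infarction and NITE) and noncardiac MAPE on disability". Noncardiac MAPE is therefore an exposure in the primary question, although it is defined among the secondary endpoints.

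Section 5.1.2 builds noncardiac MAPE from respiratory failure, sepsis or SIRS, renal failure, "Unplanned ICU admission", "Unplanned medium care admission" and reoperation. The last three stand alone, with no reference to cause. One other component does carry a reason: "Respiratory failure including pneumonia and hypoxia or hypercapnia leading to ICU admission for respiratory support".

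The same section places pulmonary embolism in MACE: "Pulmonary embolism, defined as a new thrombus within the pulmonary arterial system confirmed on CTA". The endpoint list in the Summary places it in noncardiac MAPE, whose components there include "pulmonary embolism, sepsis and/or systemic inflammatory response syndrome (SIRS), renal failure, reoperation and unplanned ICU admission".

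No section gives a rule on cause of admission, a hierarchy between the exposures, or a statement on whether they may overlap. Section 7.2 names the groups as myocardial infarction, NITE and MAPE, without the word noncardiac.

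**The concern.** A patient with a postoperative MI who is moved to the ICU because of it satisfies two of the three exposure definitions. The patient stays in the MI group and also gains the noncardiac flag. Heart failure is treated as a cardiac pathology in section 1, but non-fatal heart failure is in no MACE list, so an ICU transfer for it counts only on the noncardiac side.

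An analysis that estimates the exposures together would then adjust MI and NITE for an event that they caused, and part of their effect would be credited to noncardiac MAPE. Objective 2b has a related problem: cardiac biomarkers would be tested against a noncardiac endpoint that contains cardiac admissions. Section 4.4 pools the data with a second centre, so disagreement between the lists could also lead the two centres to code the same patient differently.

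**Working it through.** **1. The lists side by side**

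| Event | Summary, secondary objectives | Summary, endpoints | Section 2.2 | Section 5.1.2 |
|---|---|---|---|---|
| Pulmonary embolism | MACE | noncardiac MAPE | MACE | MACE |
| Stroke | MACE | in neither | MACE | MACE |
| Unplanned ICU admission, any cause | noncardiac | noncardiac | noncardiac | noncardiac |
| Unplanned medium care admission | not listed | not listed | not listed | noncardiac |
| Reoperation | not listed | noncardiac | not listed | noncardiac |

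This part needs no assumption.

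**2. Scale of the overlap**

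Inputs: 1,000 patients and 11% PMI (section 4.4); one third of PMI is MI, 19% have a MAPE, and 19% of MAPE are cardiovascular (section 1).

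- PMI = 1,000 × 0.11 = 110; MI = 110/3 = 36.7; NITE = 73.3.
- Noncardiovascular MAPE = 1,000 × 0.19 × 0.81 = 153.9.
- If a share q of MI patients gains the noncardiac flag, their share of that group is 36.7q / (153.9 + 36.7q). For q = 0.2 this is 7.3/161.2 = 4.5%; for q = 0.8 it is 29.3/183.2 = 16%. The documents do not give q.

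**3. Effect in a joint linear model of WHODAS on MI, NITE and noncardiac MAPE**

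Assumptions, none from the documents: true noncardiac MAPE in 15%, independent of PMI, adding 12 points; MI adds 25 points if admitted for the cardiac event and 5 otherwise; NITE adds 15 and 5. In the middle case 50% of MI and 20% of NITE are admitted.

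- Cause-specific coding: MI = 0.5×25 + 0.5×5 = 15.0; NITE = 0.2×15 + 0.8×5 = 7.0; MAPE = 12.0.
- Flag rate as written: no PMI 0.15; MI 1 − 0.85×0.5 = 0.575; NITE 1 − 0.85×0.8 = 0.32.
- MAPE coefficient = pooled within-group covariance of flag and WHODAS, divided by pooled within-group variance of the flag.
 - Covariance: 0.89×1.530 + 0.0367×5.015 + 0.0733×2.584 = 1.735.
 - Variance: 0.89×0.1275 + 0.0367×0.2444 + 0.0733×0.2176 = 0.1384.
 - Ratio: 12.5.
- MI coefficient = 15.0 − 12.54 × (0.575 − 0.15) = 9.7.
- NITE coefficient = 7.0 − 12.54 × (0.32 − 0.15) = 4.9.

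The same formulas for other inputs:

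| Points, MI (admitted/other); NITE (admitted/other) | Admitted, MI/NITE | MI, by cause → as written | MAPE as written (12.0 by cause) | Order of MI and MAPE |
|---|---|---|---|---|
| 25/5; 15/5 | 30%/10% | 11.0 → 7.8 | 12.5 | MI below in both |
| 25/5; 15/5 | 50%/20% | 15.0 → 9.7 | 12.5 | reverses |
| 25/5; 15/5 | 70%/30% | 19.0 → 11.6 | 12.4 | reverses |
| 15/15; 7/7 | 30%/10% | 15.0 → 12.2 | 11.1 | kept |
| 15/15; 7/7 | 50%/20% | 15.0 → 10.5 | 10.7 | near tie |
| 20/20; 10/10 | 50%/20% | 20.0 → 15.5 | 10.7 | kept |
| 25/15; 15/8 | 50%/20% | 20.0 → 15.0 | 11.8 | kept |

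MI falls in every row, by 2.8 to 7.4 points. The fall does not need admitted patients to do worse: it is also present with uniform effects.

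**4. Extra flags, middle case**

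Cardiac-cause admissions per 1,000: 0.5×36.7 + 0.2×73.3 = 33. Of these, 15% already carry a true noncardiac MAPE, so the net addition is 0.85 × 33 = 28.

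**The case against.** The strongest reply is that section 7.2 does not set out the joint model used above. It specifies a comparison of WHODAS with and without PMI, then regressions on biomarkers. The adjustment variables it names do not include noncardiac MAPE. The sample size rests on troponin elevation versus none. All of this stands: MAPE coding does not touch that comparison, and the coefficients above illustrate the section 2.1 objective rather than a written model. It does not remove the problem, because section 2.1 asks for independent effects of the three exposures and any analysis that answers it must use this definition.

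A second reply is that the components are listed separately and could be regrouped later. Regrouping needs the reason for admission, and section 5.1 lists no such item. A third is that overlap is expected, since section 1 links PMI to sepsis and to respiratory and renal failure. That is true, and some mixed-cause admissions will need judgement. It does not justify calling a purely cardiac admission noncardiac.

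Three stronger readings are tempting but unsupported:

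- **That PMI itself generates the flag through the troponin pathway.** Section 5.3 says "In case troponin-I is elevated, routine (i.e. non-study related) hospital protocol procedures involve an ECG and consultation by an anesthesiologist", with possible cardiology consultation and further tests or therapy at discretion. It mentions no ICU, medium care or monitored bed.
- **That reoperation is similarly contaminated.** Nothing in the documents suggests reoperations for cardiac causes.
- **That the ranking of the exposures will reverse.** It does so only under some of the assumed inputs.

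**Conclusion.** The point holds as a defect of definition. As worded, section 5.1.2 double-codes cardiac ICU and medium care admissions as noncardiac MAPE. This rests on the absence of any restriction on cause, not on an explicit instruction to ignore cause. The disagreement over pulmonary embolism, stroke and medium care is plain from the text.

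The consequence is a blurred contrast in the section 2.1 comparison and in objective 2b. Affected patients are not moved out of the MI or NITE groups. With 30% to 70% of MI and 10% to 30% of NITE admitted for the cardiac event, MI is attenuated by roughly 3 to 7 WHODAS points in a joint model. Those rates, the effect sizes and the 15% are assumptions, so the true size is unknown. A reader might infer that the main PMI result or the sample size is compromised; neither depends on this coding. The definition should be corrected before events are coded, but the study's powered comparison is not at risk.

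**What to change.** - In section 5.1.2, count unplanned ICU or medium care admission, and reoperation for consistency, as noncardiac MAPE only when the charted primary reason is not cardiac. Define cardiac as any MACE component, troponin elevation or heart failure. Heart failure must be named because a rule limited to MACE components would miss it.
- Add one CRF field for that reason, completed without knowledge of the 6-month WHODAS.
- Use one identical list in the Summary (both places), section 2.2 and section 5.1.2, with pulmonary embolism and stroke each in one composite only.
- Report a sensitivity analysis of noncardiac MAPE without the care-process items (ICU admission, medium care admission, reoperation).

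The cost is one field taken from the chart and aligned wording; the coding rule changes nothing in patient care. The downside is somewhat fewer noncardiac MAPE events (about 28 per 1,000 in the middle case, on assumed rates) and some judgement where causes are mixed.
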